12.3.5. Sub-Analysis for Sling Repair and Interventions for Recurrence

12.3.5.1. Subjects with only POP repair and those with sling and prolapse repair

A two sample t-test will be performed in pain score change from baseline to each follow-up visit within Xenform or native tissue repair group, to compare groups with and without SUI surgery. Using this method of analysis will make it less difficult to assess causality for adverse events, including pain.

12.3.5.2. Subjects with office-based intervention for recurrence

Adverse procedural/device event rates and QOL information will be collected for 36 months, regardless of whether or not the subject has office-based intervention for recurrence.

Event rate for each of device-related or procedure-related adverse events of specified AE type (Xenform erosion, Xenform exposure, dyspareunia) during the period after the intervention will be summarized by treatment group. Treatment groups will be compared using Cox regression for the event-free survival time (starting at the time of first office based intervention) with treatment arm.

For each QOL instrument, a comparison using t-test will be performed between native tissue repair and Xenform group on the basis of QOL score at the first scheduled follow-up after office-based intervention for recurrence.

A two sample t-test will be used to compare groups with office-based intervention for recurrence and without intervention within each treatment group. QOL score change will be reported from the last follow-up visit before office-based intervention for recurrence, to the next scheduled follow-up visit after office-based intervention for recurrence within each treatment group. For those subjects without recurrence, we will use baseline as the “before” time point in analysis, and the QOL data at 6 month follow-up visit as the “after” time point.

Similarly, event rate for each adverse device and procedure-related event type specified (mesh erosion, mesh exposure, dyspareunia), will be compared between subjects with office-based intervention for recurrence and those without. This will be done using a Cox regression of time to the first onset of each adverse event after the starting time to compare groups with office-based intervention for recurrence and within each treatment group. The starting time will be baseline for those subjects without intervention, and time of office-based intervention for recurrence for those with intervention.

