Secondary Endpoints	
1. Incidence of Xenform erosion2. Incidence of Xenform exposure3. Incidence of de novo dyspareunia4. Improvement in subject specific outcomes at 36 months compared to Baseline (pelvic floor symptoms (PFDI-20), QOL (PFIQ-7), sexual functioning (PISQ-12), TOMUS pain scale)5. Assessment of subject’s level of improvement, measured by the Patient Global Impression of Improvement for Prolapse (PGI-I for Prolapse)6. Absence of re-intervention or re-surgery for recurrence or persistence of POP or mesh exposure/erosion7. Surgical success based on the following composite outcome:
a. Subjective success: patient denies symptoms of vaginal bulging per PFDI-20 question 3, answering “no” or “yes” but “Not at all” bothersome (<2)b. Anatomic success (in the operated compartment):
• Anterior Segment: No anterior prolapse at or beyond the hymen or POP-Q point Ba<0• Apical Segment: The vaginal apex does not descend more than one-half into the vaginal canal (i.e. POP-Q point C < 1/2 TVL) for multi-compartment prolapse or POP-Q point C < 0 for single compartment apical prolapsec. No retreatment for POP (treated segment): No additional surgical treatment for POP in the segment(s) of the vagina treated at the index surgery or no pessary use since index surgery (‘treated segment’ refers to the target compartments in this study, which are the anterior and apical compartments)8. Device or procedure-related incidence of the following: pelvic pain, infection, vaginal shortening, atypical vaginal discharge, neuromuscular problems, vaginal scarring, de novo vaginal bleeding, fistula formation and/or de novo voiding dysfunction

Postmarket Study PS120081: A Prospective, Non-Randomized, Parallel Cohort, Multi-Center Study of Xenform vs. Native Tissue for the Treatment of Women with Anterior/Apical Pelvic Organ Prolapse	
Method of Assigning Subjects to Treatment	This study is a prospective, non-randomized, parallel cohort, multi-center study. Approximately 454 subjects will be enrolled and will either receive transvaginal repair with Xenform (treatment) or a native tissue repair (control) procedure. Study centers will either participate to enroll only Xenform subjects or only native tissue subjects to reduce bias; or a combination of Xenform and native tissue subjects depending on subject population and per Boston Scientific’s discretion.

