7.2. Secondary Endpoints

The secondary endpoints of the study include assessments of complications and subject reported outcomes:

1. Incidence of mesh erosion
2. Incidence of mesh exposure

3. Incidence of de novo dyspareunia
4. Improvement in subject-related outcomes at 36 months compared to Baseline ((pelvic floor symptoms (PFDI-20), QOL (PFIQ-7), sexual functioning (PISQ-12) TOMUS pain scale)
5. Assessment of subject's level of improvement, measured by the Patient Global Impression of Improvement for Prolapse (PGI-I for Prolapse)
6. Absence of re-intervention and re-surgery for recurrence of POP, persistence of disease, or Xenform exposure/erosion
7. Surgical success based on the following composite outcome:
 - a. Subjective success: patient denies symptoms of vaginal bulging per PFDI-20 question 3, answering “no” or “yes” but “Not at all” bothersome (<2)
 - b. Anatomic success (in the operated compartment):
 - Anterior Segment: No anterior prolapse at or beyond the hymen or POP-Q point Ba<0
 - Apical Segment: The vaginal apex does not descend more than one-half into the vaginal canal (i.e., POP-Q point C < 1/2 TVL) for multi-compartment prolapse or POP-Q point C < 0 for prolapse of the apical compartment alone.
 - c. No retreatment for POP (treated segment): No additional surgical treatment for POP in the segment(s) of the vagina treated at the index surgery or no pessary use since index surgery (‘treated segment’ refers to the target compartments in this study, which are the anterior and apical compartments)
8. Incidence of the following device or procedure-related AEs: pelvic pain, infection, vaginal shortening, atypical vaginal discharge, neuromuscular problems, vaginal scarring, de novo vaginal bleeding, fistula formation and/or de novo voiding dysfunction

8. Study Design

This study is a prospective, non-randomized, parallel cohort, multi-center study conducted in partnership with the AUGS PFD Registry.

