The primary endpoint will be assessed once all per protocol subjects have completed the 36 month study visit. All per protocol subjects will be followed to month 36, until study completion, or until discontinuation prior to month 36. All study procedures will be standardized for uniformity. Prior to enrolling a subject, physicians must have completed a minimum of 10 procedures (defined for each arm) in order to document competency and experience. For the native tissue arm, physicians must have completed a minimum of 10 transvaginal anterior-apical prolapse repair procedures that incorporate an apical vault suspension utilizing either a uterosacral ligament suspension or sacrospinous ligament fixation. For the Xenform arm, physicians must have completed a minimum of 10 native

tissue repair procedures (as defined for the native tissue arm) augmented with a biologic graft or Xenform, and the uterosacral and/or sacrospinous ligaments must be accessed via the anterior compartment incision. Physician training, specialty, and site procedure location (such as private-practice, hospital, academic medical center, etc.) will be recorded.

All efforts will be made to ensure all follow-up anatomic measurements (POP-Q) will be assessed by a healthcare provider to reduce surgeon bias on outcomes after the index procedure. In the event the treating surgeon is the only qualified healthcare provider at the site trained in POP-Q assessments, the follow-up anatomic measurements will be performed by the treating surgeon.

All enrolled subjects will have an anterior and/or apical defect. Concomitant procedures to treat a secondary defect can occur (including an anterior repair, posterior repair, hysterectomy, or sling placement for stress urinary incontinence) at the time of prolapse repair for the primary defect, per physician discretion. Sling placement may include a synthetic material yet a concomitant anterior repair or posterior repair cannot include a biologic graft or a synthetic implant. An anterior colporrhaphy may be required, if clinically necessary. All concomitant procedures performed will be recorded.

Subjects who undergo a medical intervention (surgical or non-surgical) to treat recurrence, persistence of POP, or Xenform or suture complication will be followed to month 36 from the initial study procedure.

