11.4.7. Months 6 (± 4 weeks), 12, 18, 24, 36 Visits ($-4/+12$ weeks)

- Pelvic exam with vaginal length measurement
- Assessment of infection (vaginal, bladder)
- Prolapse grading (POP-Q Scoring)
- Assessment of pain (TOMUS pain scale) and analgesic intake
- PFDI-20

- PFIQ-7
- PISQ-12
- PGI-I for Prolapse
- SSQ-8 for surgical satisfaction (Months 6, 12, 24, 36 only)
- EQ-5D for health status (Months 12, 24, 36 only)
- Assessment of adverse events (device, procedure, and pelvic floor related)
- Assessment of risk factors
- Study completion (Month 36 only)

All subjects who have completed the study surgery and discharge will proceed to be followed through the above-outlined study visits to Month 36 where the primary endpoint analysis will be achieved when the last subject completes this visit. All subjects completing the Month 36 visit will be considered to have completed the study.

11.5. *Re-Intervention/Re-Surgery*

It is the intention of this study to demonstrate an improvement in anterior/apical pelvic organ prolapse through clinical effectiveness of transvaginal prolapse repair with Xenform. However, it is recognized that during the course of the study, there is a possibility subjects may require a medical re-intervention for events including but not limited to failed prolapse repair, persistence of prolapse symptoms, or Xenform or procedure-related complication. A re-intervention may include surgical or non-surgical treatments and can occur for a medical complication or for prolapse recurrence. For the purpose of this study surgical interventions shall be classified as “re-surgery” and non-surgical interventions shall be classified as “re-interventions”. Analyses will be performed to compare the rate of office-based interventions and of surgical interventions for medical complications and for prolapse recurrence in both treatment groups.

Non-surgical interventions (re-interventions) are defined as office-based procedures and do not involve an operating room procedure. Examples of non-surgical interventions may include but are not limited to an office visit to trim exposed Xenform or suture in the vagina, a pessary, or physical therapy to treat procedural complications or persistent prolapse symptoms. Data on non-surgical interventions will be captured in the CRFs. Subjects will continue to be followed per the regular study visit schedule.

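### Section 12.3.5.2 plans a between-arm Cox regression for Xenform erosion and exposure, which control women cannot have under assigned treatment, and the plan switches between 'mesh' and 'Xenform' when naming these events

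*Combined protocol and SAP*

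**What the plan says.** **The planned comparison.** Section 12.3.5.2 deals with women who have an office-based intervention for recurrence. It lists the event types to be analysed afterwards ("Xenform erosion, Xenform exposure, dyspareunia) during the period after the intervention will be summarized by treatment group"). That sentence only summarises by arm; the next one makes the comparison: "Treatment groups will be compared using Cox regression for the event-free survival time", with time counted from the first office-based intervention and treatment arm in the model. Two paragraphs later the same section calls the events mesh erosion and mesh exposure, and plans a second Cox regression, within each arm, of women with an intervention against women without. Section 12.3.5.3 repeats these analyses for surgical intervention for recurrence. Section 12.3.7 repeats them for re-surgery for complications or recurrence.

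**What control women receive.** Section 8.2.2 defines the control as native tissue repair. Section 8 bars a biologic graft or synthetic implant from a concomitant anterior or posterior repair, but for slings it says "Sling placement may include a synthetic material".

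**The terms in the endpoint lists.**

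| Endpoint | Synopsis | Section 7.2 | Section 12.1.2 |
|---|---|---|---|
| 1 (endpoint 2, exposure, follows the same pattern) | "Incidence of Xenform erosion" | "Incidence of mesh erosion" | Xenform |
| 6 | "Absence of re-intervention or re-surgery for recurrence or persistence of POP or mesh exposure/erosion" | "Absence of re-intervention and re-surgery for recurrence of POP, persistence of disease, or Xenform exposure/erosion" | Xenform |

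**The concern.** A Cox regression on treatment arm estimates how much more often an event occurs in one arm than in the other. If women in one arm do not carry the material that defines the event, there is nothing to estimate. The output would be a failed fit, a very large and meaningless hazard ratio, or a score-test p-value that could be misread as a finding about the device's safety. Evaluating Xenform-related complications is a stated secondary objective (Section 6), so these rates should be reported in a form that can be interpreted.

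The wording problem is separate. If 'mesh' is read literally, a sling exposure could count as an event in either arm. If it means Xenform, it cannot. The documents do not define the term, so two analysts could count different events.

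**Working it through.** **Figures in the plan.** The plan gives no rate, margin, event count or sample size for erosion or exposure, so there is none to reproduce. The only event in the list that is sized is de novo dyspareunia (Section 12.1.2.2: 9%, margin 7.9%, type I error 0.05, power 80%). It reproduces: n = (1.645 + 0.842)² × 2 × 0.09 × 0.91 / 0.079² = 162.3, so 163 per arm, as stated. Dyspareunia can occur in both arms and is not part of the problem.

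**The between-arm hazard ratio.** Suppose m women per arm are at risk and all k events fall in the Xenform arm, with no censoring before the last event. Both m and k are assumptions. At each event there are x Xenform women at risk (m, m − 1, and so on) and m controls. The log partial likelihood in the log hazard ratio b is the sum over events of b − log(x·e^b + m). For m = 20, k = 4:

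| b | log partial likelihood |
|---|---|
| 0 | −14.601 |
| 2 | −12.212 |
| 5 | −11.693 |
| 10 | −11.664 |
| 20 | −11.664 |

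It rises towards its limit, −log(20 × 19 × 18 × 17) = −11.664, and has no maximum. No finite hazard ratio or Wald interval exists. A software fit of this example stopped with a singular matrix.

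**The score (log-rank) test.** This can still be computed. With p = x/(x + m) at each event, Z = Σ(1 − p) / √Σp(1 − p). For m = 20, k = 4 the values of p are 0.500, 0.487, 0.474 and 0.459, so Z = 2.080/√0.9975 = 2.08.

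| k (all in the Xenform arm) | Z, m = 20 | two-sided p |
|---|---|---|
| 1 | 1.00 | 0.32 |
| 2 | 1.43 | 0.15 |
| 4 | 2.08 | 0.037 |
| 6 | 2.63 | 0.009 |

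At k = 4 the result hardly depends on m: p = 0.029 for m = 10 and 0.041 for m = 40. Z is roughly √k. The test therefore counts Xenform events and compares them with a group that could not have any.

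**The within-control comparison.** If 'mesh' means Xenform, the second Cox regression in Section 12.3.5.2 has no events in the control arm, with or without an intervention.

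**Extent.** Two event types in three sections (12.3.5.2, 12.3.5.3, 12.3.7) make 2 × 3 = 6 between-arm comparisons that fail as written, counting one set per section.

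**What 'mesh' could add.** The documents give no sling share and no sling exposure rate. Assuming that 20% to 60% of 227 controls have a synthetic sling and that 1% to 4% of those have an exposure, a literal 'mesh' count for endpoints 1 and 2 would include between 227 × 0.20 × 0.01 = 0.5 and 227 × 0.60 × 0.04 = 5.4 control women. Under 'Xenform' the expected count is 0. This is an illustration only.

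**The case against.** **These analyses are minor.** They are unsized sub-analyses in post-intervention subgroups, and Section 12.1.2.1 sets no between-arm hypothesis for erosion or exposure. A competent analyst would see no control events and report descriptively. That is fair and limits the consequences, but the plan states an analysis that cannot be carried out, and correcting it costs almost nothing.

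**Zero is not absolute.** The ITT set keeps women whatever treatment they received (Section 12.2.1), and nothing bars Xenform at a control woman's re-surgery, which matters most for Sections 12.3.5.3 and 12.3.7. This stands. The claim is therefore limited to assigned treatment. A few such events would make a hazard ratio computable but not a comparison of the two repairs.

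**'Mesh' probably means Xenform.** Sections 12.1.1.1, 12.2.3, 12.3.3, 12.3.4 and 12.3.8.1 use the word for the treatment arm, and Section 19.2.1 and Table 21.6-1 name Xenform exposure and erosion. A reader might infer that the event counts do change with the section followed. The documents do not show that; on the likelier reading this is loose terminology. It is still unsettled in the text, because Section 12.1.2 points to Section 21.2 for definitions, and Table 21.2-1 defines neither event. Section 21.1 refers to a dictionary in the Manual of Operations, which may resolve it.

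**Endpoint 6 and sutures.** Section 11.5 gives "an office visit to trim exposed Xenform or suture in the vagina" as an example of a non-surgical intervention, and Section 8.2.2 allows permanent sutures. A reader might infer that the Xenform wording of endpoint 6 biases the comparison against the Xenform arm. The documents do not support this. That wording leaves out suture exposure in both arms, endpoint 6 has no between-arm hypothesis, and Sections 12.3.3 and 12.3.4 compare interventions for complications without restricting them to Xenform.

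**Conclusion.** The point holds for two of the three event types named in Section 12.3.5.2. Under assigned treatment, control women have no Xenform erosion or exposure, so the between-arm hazard ratio is not estimable in Sections 12.3.5.2, 12.3.5.3 and 12.3.7, and a score test would only show that controls have no graft. If 'mesh' means Xenform, the within-control comparison is empty as well. The non-estimability rests only on there being no control events; the p-values rest on the assumed numbers at risk and events.

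The inconsistent terms are a matter of fact. Any effect on the counts is possible but not shown. Dyspareunia, the co-primary tests and the sample size are untouched. It is a correction worth making before the final analysis, not a threat to the study's main conclusions.

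**What to change.** 1. Use 'Xenform' for endpoints 1, 2 and 6 in the synopsis, Section 7.2 and Section 12.1.2, and throughout Section 12.3.5.2.
2. Report Xenform erosion and exposure in the Xenform arm only, as a proportion with an exact confidence interval.
3. Remove these two event types from the between-arm and within-control Cox comparisons in Sections 12.3.5.2, 12.3.5.3 and 12.3.7. Keep dyspareunia in all of them. The within-Xenform comparison can stay.
4. Tabulate any sling-mesh or suture exposure separately and descriptively by arm, where recorded. Do not redefine endpoint 6: enrolment closed in December 2016 (Table 10.1-1), and adding suture events now would change a secondary endpoint late in the study.

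The cost is a wording change in the protocol and SAP. No new data are needed and no estimable comparison is lost. The separate table may be incomplete, because suture and sling exposure are not named in Table 21.6-1 and the documents do not say what is recorded for controls shared from the registry.

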Propensity score adjusted confidence intervals described in Section 12.2.3 (Propensity Score Methodology) will be used to evaluate continuous variables including QOL score improvements between two groups.

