12.2.2. Control of Systematic Error/Bias

To reduce selection bias in this non-randomized study, each study center will be permitted to enroll subjects in only one of the treatment groups. Physicians will be selected based on device and clinical research experience and the decision as to which device to implant in subjects prior to study initiation at each center. Some study centers may be permitted per Boston Scientific to enroll subjects in both treatment and control groups. All decisions will be documented prior to subject enrollment. All subjects meeting the eligibility criteria at the study center will be screened and enrolled as applicable.

Propensity score stratification will be utilized to address the potential imbalance in risk factors between groups, described in Section 12.2.3 (Propensity Score Methodology). This analysis will be performed blind to all clinical outcome data and prior to performing any analysis of endpoints.

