12.2.3. Propensity Score Methodology

Analyses comparing the treatment groups will be adjusted for the propensity score. The propensity score is the probability that the subject enrolled in the mesh arm rather than the native tissue (control) arm, given the characteristics of the subject and center. The characteristics identified are as follows: age, race, body mass index, smoking, diabetes, post-menopausal, prior prolapse repair, prior hysterectomy, estrogen use, POP-Q C measurement, POP-Q Ba measurement, POP-Q Bp measurement, concomitant repair for stress urinary incontinence, and surgeon case volume. Logistic regression of both treatment arms (i.e., (transvaginal biologic mesh repair vs. native tissue repair) on these characteristics will be used to estimate the propensity score. The subjects will then be partitioned into five strata corresponding to quintiles of the propensity score. If the balance between treatment arms within the strata is deemed adequate, the treatment difference adjusted for propensity score stratum will be estimated as described in the following.

The propensity adjusted treatment difference will be based on averaging the treatment differences of the propensity score strata. For a binary outcome, the within-stratum treatment difference is $D_j = p_{T_j} - p_{C_j}$, where p_{T_j} and p_{C_j} is the proportion of treatment and control subjects, respectively, in stratum j . The variance of D_j is approximately

$$V_j = \frac{p_{T_j}(1 - p_{T_j})}{n_{T_j}} + \frac{p_{C_j}(1 - p_{C_j})}{n_{C_j}}$$

Denoting the number of subjects in stratum j by $n_j = n_{T_j} + n_{C_j}$, the treatment difference will be estimated by the (weighted) mean of the within-stratum treatment differences

$$D = \sum_j \frac{n_j}{n} D_j$$

where $n = \sum_j n_j$ is the total sample size across all strata and study arms. D is approximately normally distributed with variance

$$V = \sum_j \left(\frac{n_j}{n}\right)^2 V_j$$

from which a confidence interval for the true treatment difference will be constructed. For each continuous outcome, the confidence interval will be constructed similarly, with D and V obtained as above with the treatment difference within each stratum replaced by $D_j = \bar{X}_{T_j} - \bar{X}_{C_j}$, where \bar{X}_{T_j} and \bar{X}_{C_j} , respectively, is the mean of the treatment and control subjects, and

$$V_j = \frac{S_{T_j}^2}{n_{T_j}} + \frac{S_{C_j}^2}{n_{C_j}}$$

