12.3.5.3. Subjects with surgical intervention for recurrence

The above mentioned analyses for the subgroup with office based intervention for recurrence will be repeated for subjects with surgical intervention for recurrence.

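### The re-intervention sub-analyses compare Xenform with native tissue by a t-test and a Cox model that name no propensity adjustment, against the plan's own rule for arm comparisons

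*Combined protocol and SAP*

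**What the plan says.** The study is non-randomized, and the plan relies on the propensity score to make the arms comparable. Section 12.2.2 gives the reason: "Propensity score stratification will be utilized to address the potential imbalance in risk factors between groups". Section 12.2.3 makes it a general rule: "Analyses comparing the treatment groups will be adjusted for the propensity score". It defines the adjustment as five quintile strata whose within-stratum differences are averaged with weights, with formulas for binary and continuous outcomes. Section 12.1.2.3 repeats the rule for secondary outcomes, saying that propensity-adjusted intervals "will be used to evaluate continuous variables including QOL score improvements between two groups". Sections 12.3.2 and 12.3.4 apply it to the intervention rates, and 12.3.6 applies it to EQ-5D and SSQ-8.

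Section 12.3.5.2 concerns women who had an office-based intervention for recurrence. It contains two comparisons of Xenform with native tissue:

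- For each QOL instrument, at the first scheduled visit after the intervention, "a comparison using t-test will be performed between native tissue repair and Xenform group on the basis of QOL score".
- For device- or procedure-related erosion, exposure and dyspareunia, "Treatment groups will be compared using Cox regression for the event-free survival time (starting at the time of first office based intervention) with treatment arm".

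The section also contains comparisons inside each arm, for example "A two sample t-test will be used to compare groups with office-based intervention for recurrence and without intervention within each treatment group".

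Section 12.3.5.3 says the analyses "will be repeated for subjects with surgical intervention for recurrence". Section 12.3.7 carries the 12.3.5 sub-analyses to re-surgery for complications or recurrence.

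**The concern.** The plan gives two instructions for one kind of comparison. An analyst who follows 12.3.5.2 to the letter reports arm differences with no control for the characteristics that 12.2.3 lists, in a study where site, physician and patient mix can all differ by arm. An analyst who follows 12.2.3 cannot run the named t-test. Whichever instruction is set aside, the choice is made after the data are in.

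The stakes are modest. These comparisons have no margin, alpha level or power statement. But they would be the study's evidence on how women fare after re-intervention in each arm, and a reader would expect them to be handled like the other arm comparisons.

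**Working it through.** **1. Text comparison.**

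| Comparison between arms | Section | Propensity adjustment named? |
|---|---|---|
| Primary effectiveness and safety | 12.1.1.3 | Yes |
| QOL improvement and other continuous outcomes | 12.1.2.3 | Yes |
| Intervention rates, recurrence and complications | 12.3.2, 12.3.4 | Yes |
| EQ-5D, SSQ-8 | 12.3.6 | Yes |
| QOL after office-based intervention | 12.3.5.2 | No: t-test |
| Adverse events after office-based intervention | 12.3.5.2 | No: Cox, treatment arm the only named term |
| The same, after re-surgery | 12.3.5.3, 12.3.7 | No: methods repeated |

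No section exempts the last three rows or calls them unadjusted by design.

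**2. Does 12.2.3 silently govern?** For the t-test, no. The 12.2.3 estimator is a weighted mean of stratum differences with its own variance, which is a different procedure. For the Cox model, 12.2.3 could be read as applying, but it has no time-to-event formula, so the analyst would have to invent the method.

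**3. Can the five strata be used here?** The documents give no rate of intervention for recurrence, so 5%, 10% and 20% are assumed, with the 227 per arm of Section 12.1.1.2.

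- Women per arm: 227 × 0.05 = 11.4, 227 × 0.10 = 22.7, 227 × 0.20 = 45.4.
- Per arm-by-stratum cell, if evenly spread (divide by 5): 2.3, 4.5, 9.1.
- A within-cell variance needs at least two women. With 11 per arm, all five cells in an arm reach two only when four cells hold 2 and one holds 3: 5 × 11!/(2!⁴ × 3!)/5¹¹ = 0.0426. For both arms this is 0.0426² = 0.0018, so the chance that at least one of the 10 cells falls short is about 99.8%.
- By the same reasoning the chance is about 35% with 23 per arm and under 1% with 45.

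The plan's own 1% rate of surgical intervention for complications (12.3.4) gives 227 × 0.01 = 2.3 women per arm from that source. Stratification may therefore be unworkable, and in the smallest subgroups no model will fit.

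**4. What could leaving out the adjustment do?** Suppose confounding shifts mean QOL by b SD. With k women per arm, δ = b/√(2/k), and the true rejection rate of a nominal two-sided 5% test is 1 − Φ(1.96 − δ) + Φ(−1.96 − δ). Both b and k are assumed.

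| k per arm | b = 0.2 | b = 0.3 |
|---|---|---|
| 11 | 7.6% | 10.8% |
| 23 | 10.4% | 17.4% |
| 45 | 15.8% | 29.6% |

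**5. Cost of a single covariate.** If the propensity score differs between arms by an assumed d SD and is unrelated to the outcome, the variance of the arm difference is multiplied by about 1 + d²/4. This is 1.06 at d = 0.5 and 1.25 at d = 1.0, and somewhat more in samples this small.

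**The case against.** The strongest reply is that this is a wording mismatch in sub-analyses that carry no formal inference, and that one sentence calling them descriptive exceptions would cure it. Much of that stands: such a sentence would remove the contradiction. It would still leave arm comparisons exposed to the confounding that the propensity score was introduced to address, when a one-covariate adjustment is cheap.

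A second reply is that the Cox text does not exclude other terms. That is right. The plan is silent there, and only the t-test is a firm contradiction.

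Third, propensity adjustment is only a partial remedy. The score models arm membership from 14 baseline, concomitant-repair and surgeon characteristics. It does not model which women go on to re-intervention, an event that occurs after treatment. This also stands, and is why the results should be labelled exploratory.

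Fourth, two of the three named event types, Xenform erosion and exposure, presuppose the device. An arm hazard ratio for them has no useful meaning with or without adjustment, so the Cox adjustment matters for dyspareunia only.

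A reader might also infer that the between-arm test is biased because it ignores the QOL score at the last visit before the intervention, which the same section uses for its change scores, and that covariance adjustment for that score is therefore required. The documents do not support this. That visit comes after the index surgery, so an arm gap in the score may itself be an effect of the procedure. Adjusting for it asks a different question, and no gain in precision can be promised once the propensity score is also in the model.

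**Conclusion.** The concern holds. Section 12.3.5.2, and by repetition 12.3.5.3 and 12.3.7, prescribes a between-arm QOL comparison that cannot be reconciled with the rule in 12.2.3. It also prescribes a between-arm Cox model for which the plan states no adjustment and supplies no method.

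The size of any resulting bias cannot be derived from the documents, because they give neither the subgroup sizes nor the imbalance. The rejection rates above only show the order of effect under assumed shifts of 0.2 to 0.3 SD and 11 to 45 women per arm.

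Two wider inferences should be avoided. The comparisons of women with and without intervention inside each arm do not compare treatment groups, so the rule does not reach them. The primary endpoints, the overall QOL comparisons and the intervention rates are already propensity adjusted, so the study's main conclusions are untouched. This is a minor but worthwhile correction.

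**What to change.** In 12.3.5.2, with matching wording in 12.3.5.3 and 12.3.7:

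- Replace the between-arm QOL t-test with a linear model containing treatment arm and the propensity score as a single covariate. Use the score already estimated on the full cohort before endpoint analysis, and state its scale.
- Add the same covariate to the between-arm Cox model for dyspareunia.
- Summarise Xenform erosion and exposure in the Xenform arm only, with no arm hazard ratio.
- Label these comparisons exploratory, and state that adjustment for baseline characteristics does not remove selection into re-intervention.
- When an arm has too few women to fit the model, report descriptive results by arm only, with the minimum number fixed in advance.
- Adjustment for the last pre-intervention QOL score may be added as an optional sensitivity analysis, with a note that the score is measured after treatment.

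Add a line in 12.2.3 saying that these sub-analyses use the score as a covariate because five strata may be too sparse, and that this is also the time-to-event method. Leave the within-arm comparisons as they are.

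The cost is a few sentences and minor code, with no new data. The downside is some loss of precision in small subgroups, as sized in step 5 of the working.
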